**SYNOPSIS**

Title of Study	Safety and efficacy of concentrated autologous concentrated bone marrow aspirate (BMAC) in preventing wound complications in amputations
Objectives	

• Determine the safety and explore efficacy of BMAC in preventing wound complications in amputations.

• Characterize the host tissue response to, paracrine activity of, and fate of transplanted BMAC.

• Determine the effects of chronic limb ischemia and diabetes on nerve function and to assess the effects of mesenchymal stem cell administration on their function.

Planned Number of Subjects and Duration of Involvement	12 patients, 12 month follow up period
Patient Population	Critical limb ischemia (CLI) patients scheduled for amputation
Investigational Product Name	Concentrated autologous bone marrow aspirate (BMAC)
Methodology Overview	
This is an open label pilot trial.
 
Up to twelve (12) patients scheduled for amputation will receive bone marrow cells concentrated (BMAC) via the BioCue™ Platelet Concentration Kit device injected IM at 25 sites in the leg proximal to the amputation in the index limb to prevent ischemic wound complications after surgery. BMAC will be injected into the anterior tibialis muscle (ATM) below the point of amputation for analytical purposes. Patients will be scheduled for amputation at Day 7 post injection. Safety will be evaluated by review of treatment related adverse events (AE) during the 12-month follow-up period. In subjects undergoing BKA, we will compare rates of wound complications and conversion from BKA to AKA to historical controls at our institution to assess trends in therapeutic efficacy.
 
Patients will undergo amputation and injection sites will be harvested from the ATM at that time. Immunohistochemical staining (IHC) will determine capillary density and local host immune responses. Angiogenic and inflammatory cytokines will be quantified using a multiplex array system and quantitative polymerase chain reaction (PCR).

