## **4 STUDY OVERVIEW**

### **4.1 Study Approach**

This protocol is designed to describe a Phase I single center open label trial study that will enroll up to 12 patients requiring semi-elective amputation within a 30-day period for complications related to CLI.

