#### **6.1.2 Safety issues**

Safety of the BioCue™ device to concentrate BMA for the prevention of wound complications in amputation will be determined by review of treatment related adverse events (AE) and serious adverse events (SAE) during the study period of 12 months by the Data Safety Monitoring Board (DMSB) appointed by the Clinical and Translational Sciences Institute (CTSI) at the Indiana School of Medicine or Data Safety Committee (DMC) designated by the Principal Investigator.

The BMAC dose proposed in this trial was selected based on prior clinical trials. We may not see any evidence of efficacy in our composite endpoint, which may reflect an inadequate dose or sample size. In this case we would propose a future study exploring escalating doses of BMAC. In the instance of evolving infection, we would re-assess our inclusion/exclusion criteria and evaluate the contribution of pre-amputation procedures on the lower leg. Patients may request earlier amputation due to worsening rest pain or anxiety. Consideration for amputation sooner than one week post injections will be determined by the PI based on the severity of the subject's condition, so as to offer this research as an option to all eligible subjects.

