### **9.3 Planned Analyses**

The clinical study report will contain only summary data analyses reflecting safety profiles, and summary data analyses of efficacy. All patient data will remain coded during analyses to maintain patient confidentiality.

The data management center for this trial will be at the CTSI, or a Data Monitoring Committee (DMC) will be appointed by the Principal Investigator. We will use a web-based HIPAA compliant online system for data entry and data management, as we are currently doing in our current clinical trials. Data will be collected from each enrolled patient using a comprehensive case report form and uploaded into a specifically designed database in the OnCore Enterprise Clinical Trial Management System and VA REDCap system. All the data will be analyzed and generated using SAS.

**Safety Assessment.** Primary attention will focus on the safety of the administration of BMAC as measured by treatment-related AEs. Treatment-related AEs will be categorized overlapping systems and severities. Three categories of systems are cardiovascular, respiratory, or infectious. Two categories of severity will be serious adverse (SAE) and major adverse cardiac events (MACE). For completeness, instances of AEs may appear in more than one category. Within each of these categories AEs will be listed in descending order of frequency for the treatment group. In addition, for each category, the sum and difference between the two routes of delivery of the proportions will be reported as percent incidence. Binomial confidence Intervals at the 95% confidence level and *p*-values for these 3 groups will be calculated. Since previous trials have not reported AEs with BMAC treatment, confidence intervals will be generated by the method of the Wilson Score Interval because they are robust, with good coverage probability even for small number of trials and are not degenerate near zero. These intervals will be used to summarize the data rather than as any formal inferential statement and to assist the Data Monitoring Board in their deliberations. No adjustment for multiplicity will be made.

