## **10 ADVERSE EVENT REPORTING**

### **10.1 Adverse Events**

Reporting of adverse events will comply with federal regulations for IDE safety reporting. AEs occurring during the enrollment period should be documented by the Investigator in progress notes but will not

be collected or analyzed by Indiana University School of Medicine unless considered serious and research related by the Investigator. The MedDRA scale will be used to describe adverse events.

Serious adverse events (SAEs) related to the research treatment that are encountered during study enrollment will be documented by the Investigator and reported to Indiana University School of Medicine within 72 hours upon discovery. SAEs are defined under current cGCP guidelines as events that result in one or more of the following:

- life-threatening illness or injury;
- permanent impairment of a body structure or a body function;
- medically necessary in-patient hospitalization;
- medical or surgical intervention necessary to prevent permanent impairment to body structure or function; or
- fetal distress, fetal death, or congenital abnormality.

Serious events that affect the rights, safety, or welfare of subjects must be documented on a form and be reported within 72 hours to Indiana University School of Medicine and to the Investigator's IRB according to that IRB's policies.

Any potential deficiencies with the BioCue™ devices (including, but not limited to deficiencies in packaging, labelling, and/or device processing) will be reported to Zimmer Biomet for evaluation.

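### The safety analysis counts only adverse events judged treatment-related, in an open-label, uncontrolled trial with amputation about a week after injection, and plans no all-cause AE table

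*Combined protocol and SAP*

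**What the plan says.** The Safety Assessment paragraph of Section 9.3 opens with "Primary attention will focus on the safety of the administration of BMAC as measured by treatment-related AEs". The system and severity categories, listings, percentages and Wilson intervals that follow are all built on that set. The Synopsis uses the same definition: "Safety will be evaluated by review of treatment related adverse events (AE) during the 12-month follow-up period". Section 3 and the objective paragraph in Section 7.1 repeat it, so this is the plan's settled approach and not a slip of wording.

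On who judges relatedness, Section 10.1 has AEs noted in progress notes but says they will not "be collected or analyzed by Indiana University School of Medicine unless considered serious and research related by the Investigator". Section 6.1.2 gives safety review to a board appointed by the CTSI "or Data Safety Committee (DMC) designated by the Principal Investigator", but neither body is asked to attribute or re-attribute events.

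On design, the Synopsis states "This is an open label pilot trial" and Section 4.1 describes a "Phase I single center open label trial study that will enroll up to 12 patients". There is no concurrent control. On timing, the Synopsis says "Patients will be scheduled for amputation at Day 7 post injection"; elsewhere this is approximately one week, and Section 6.1.2 lets the PI consider an earlier amputation. Section 9.2, on bias minimization, covers enrollment order only.

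**The concern.** Determining safety is part of the first objective, and Section 3 says the results will frame a Phase II trial. A rate limited to treatment-related events is the product of two things: how often events happen, and how often someone attributes them to BMAC. Here the second factor has little to anchor it. There is no masking, no control arm and no stated causality criteria, and a major operation on the same limb follows within about a week. Section 11.1 lists pain, bleeding and infection as risks after the surgical procedure. Section 7.3.2 treats infection, bleeding and tissue reaction at the index site as reasons to suspend enrollment. The same event types can thus come from either source. The cardiovascular, respiratory and infectious categories of Section 9.3 are equally open to explanation by surgery or vascular disease.

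At stake is a safety summary that could stay near zero whatever happens to the subjects, with no all-cause figure beside it.

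**Working it through.** **1. No figure to reproduce.** The documents give no expected AE rate, no acceptable limit and no derivation of N = 12. What follows is a reading of the text and an illustration.

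**2. Which events escape the relatedness filter**

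| Event | Recorded regardless of relatedness? | Where it is reported |
|---|---|---|
| Wound infection, minor and major stump revision | Yes (7.1; Table 4 checks infection from Day 3 to Week 52) | Wound complications |
| Revision of amputation | Yes (7.1, Table 4) | 12-month rate against historical controls; 6-month composite |
| Gangrene, death | Yes, as parts of the 6-month composite (9.3); gangrene also in Table 4 | Exploratory efficacy, against historical cohorts |
| Non-fatal cardiac, respiratory and systemic infectious events | No all-cause summary planned | Safety tables in 9.3, treatment-related only |

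**3. Sections 9.3 and 10.1 side by side.** Section 9.3 has SAEs as one category among treatment-related AEs, so it expects non-serious related events as well. Section 10.1 collects and analyzes only events that are both serious and research related. The filter in 10.1 is the narrower of the two and acts first, so a change to 9.3 alone would lack data.

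**4. Illustration with Wilson 95% intervals.** The method and level are those of Section 9.3; n = 12 is from Section 4.1; the counts are assumed. With p = x/n, z = 1.96 and z² = 3.8415, the limits are

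[p + z²/(2n) ± z·√(p(1 − p)/n + z²/(4n²))] / (1 + z²/n).

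- 0/12: the lower limit is 0; the upper limit reduces to z²/(n + z²) = 3.8415/15.8415 = 24.2%.
- 4/12: (0.3333 + 0.1601)/1.3201 = 0.3737; half-width 1.96 × √(0.01852 + 0.00667)/1.3201 = 0.2356; interval 13.8% to 60.9%.

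If 4 of 12 subjects had a Grade 3 or higher event and all four were attributed to surgery, the plan would report the first line and an all-cause table the second.

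**5. How far attribution alone moves the result.** Let b be the all-cause rate per subject and q the share attributed to BMAC. The reported rate is b × q, and with independent subjects the chance of an empty table is (1 − bq)^12. The documents do not give q. For scale, b = 19% is the upper figure for BKA-to-AKA conversion in Section 1. That event is itself recorded unfiltered, so the figure only borrows a size. A second row assumes b = 50%.

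| b | q = 1 | q = 0.5 | q = 0.25 | q = 0.1 | q = 0 |
|---|---|---|---|---|---|
| 19% | 8% | 30% | 56% | 79% | 100% |
| 50% | <0.1% | 3% | 20% | 54% | 100% |

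For example, at b = 19% and q = 0.25: (1 − 0.0475)^12 = 0.558. Counted regardless of attribution at 19%, 12 × 0.19 = 2.28 subjects with an event are expected, and the chance of at least one is 1 − 0.81^12 = 92%.

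**The case against.** Much of the risk is covered elsewhere. Stump infection, revision, gangrene and death carry no relatedness filter. The 12-month revision rate and the 6-month composite are set against historical controls. A reader might infer that the trial yields nothing comparable with other amputation patients, or that deaths and stump infections would vanish. The documents do not support either inference. What remains is that these outcomes are not presented as safety, and that non-fatal cardiac, respiratory and systemic infectious events have no such route.

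Section 7.3.2 suspends enrollment on a wider standard that includes possible relatedness, for Grade 3 or higher infection, bleeding or tissue reaction at the index site. Section 10.1 also sends serious events affecting subjects' rights, safety or welfare to the sponsor and IRB within 72 hours, with no relatedness condition in that sentence. Section 6.1.2 can be read as board review of all SAEs, though its wording is ambiguous. These provisions stand as oversight, but none changes what Section 9.3 tabulates.

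It is also tempting to say that the Investigator's judgement decides the termination trigger. Section 7.3.2 makes termination depend on relatedness but does not say who judges it. Likewise, the option of a PI-designated committee is a governance matter; no section gives either body the task of attribution.

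Finally, Section 9.3 says the intervals are descriptive, and in 12 uncontrolled subjects an all-cause rate cannot isolate harm from BMAC. Both points are right. They limit what any table can show, but do not justify having only the filtered one.

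**Conclusion.** The concern holds for the planned safety analysis. As written, Section 9.3 reports a rate that can lie anywhere from zero to the full all-cause rate depending on attribution, in a design that gives attribution little support. In the assumed example the difference is 0/12 (0 to 24.2%) against 4/12 (13.8% to 60.9%).

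This rests on the text of Sections 9.3 and 10.1 and on the absence of any planned all-cause AE table. The counts and attributed shares are assumptions, shown as a range; they do not predict under-attribution in this trial. The point does not extend to the stump, gangrene and death outcomes, which are counted regardless of relatedness, nor does it suggest that BMAC is harmful. It should be corrected, at modest cost.

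**What to change.** - **Section 9.3:** make the main safety table all AEs and SAEs regardless of attribution, counted as subjects with at least one event, with Wilson 95% intervals. Split it by onset before and after amputation. Include deaths and stump events, and show those judged related or possibly so in a secondary column. Align the Synopsis, Section 3 and Section 7.1.
- **Section 10.1:** amend in parallel so that all AEs are collected and analyzed. This also removes the mismatch with Section 9.3 over non-serious events.
- **Table 4:** AE/SAE evaluation runs from the injection visit to Week 24 and is absent from the Week 52 call. Either add AE/SAE questions to that call or state that the AE table ends at Week 24.

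The cost is more AE data entry and coding for up to 12 subjects, a few added questions at an existing call, longer tables and probably a less favorable headline rate. No new visits are needed. The report should say plainly that the all-cause rate does not by itself separate BMAC effects from those of surgery and disease.

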### **7.3.2 Suspension or premature termination of the study**

This study may prematurely terminate at any time because of a regulatory authority decision, a change in opinion of the IRB, or at the discretion of the Investigator or Sponsor. The study will be terminated in the event of a Grade 4-5 unexpected and research related event based on the Common Terminology Criteria for Adverse Events (CTCAE), version 4.0. Enrollment will be temporarily suspended for any related or possibly related post-BMAC injection and post-amputation infection, bleeding or tissue reaction at the index site that are  $\geq$  Grade 3. If this trial is temporarily suspended or prematurely discontinued, Indiana University School of Medicine will promptly notify the Investigator(s) and provide instructions. If the study is temporarily suspended, Indiana University School of Medicine will provide guidance on timing and procedures for resuming the study. If the study is prematurely discontinued, all study materials must be collected and all study forms completed to the extent possible. All such materials must be returned to Indiana University School of Medicine upon request with an explanation of the circumstances that led to termination.

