## **11** RISK ANALYSIS

### **11.1** Potential Risks of the Investigational Product and Clinical Investigation

The types of risk associated with IM injection are notably rash, mild fever, and myalgia. These risks are mild and rare. These risks are all stated in the consent form.

Further risks include pain, bleeding, and infection following the surgical procedure. Additionally, as with any other surgical procedure, the investigational device may be dropped in the surgical theater. Flash sterilization will not be allowed, and additional sterile devices will be available to prevent procedure termination with minimal delay.

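### Non-serious, non-infectious local adverse events have no category in the section 9.3 safety tables, although index-site bleeding and tissue reaction of Grade 3 or higher suspend enrollment under 7.3.2

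*Combined protocol and SAP*

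**What the plan says.** On the safety measure, section 9.3 states: "Primary attention will focus on the safety of the administration of BMAC as measured by treatment-related AEs". It then sets the classification. For body systems: "Three categories of systems are cardiovascular, respiratory, or infectious". For what it calls severity, it gives two classes, SAE and MACE. An event may fall in several classes: "For completeness, instances of AEs may appear in more than one category". Output is organized by class: "Within each of these categories AEs will be listed in descending order of frequency for the treatment group". Percent incidences are also reported for each category, with 95% Wilson score intervals meant to describe the data and help the monitoring board. Nothing is said about an event that fits no category, and the study report is limited to summary analyses.

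The events the protocol expects are named elsewhere. Section 11.1 says: "The types of risk associated with IM injection are notably rash, mild fever, and myalgia". It describes these as mild and rare, and adds pain, bleeding and infection after the surgical procedure. Section 7.3.2 suspends enrollment for related or possibly related "infection, bleeding or tissue reaction at the index site that are" Grade 3 or higher. The grades there are CTCAE version 4.0.

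Three places bear on which events reach the tables. Section 6.1.2 has the board judge safety from treatment-related AEs and SAEs over 12 months. Table 4 schedules AE/SAE evaluations at Visits 2 to 9. Section 10.1 has the investigator note AEs in progress notes, but they are not collected or analyzed unless serious and research related. It also says: "The MedDRA scale will be used to describe adverse events".

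**The concern.** The treatment is local. Up to 25 proximal sites and the anterior tibialis muscle are injected, after marrow is drawn from the iliac crest. The safety tables are nevertheless built around cardiovascular, respiratory and infectious events. A treatment-related bleed, tissue reaction, rash, myalgia or pain that is not serious has no row to be counted in and no interval.

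Safety is part of the first objective, and these tables are the only safety summary that the plan describes. They also do not line up with the suspension rule. That rule works on CTCAE grade and on local events, whereas the tables work on seriousness and on three systems, two of which have no link to the injection site. A reader of the study report could not recover from the tables the events that led to a suspension.

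**Working it through.** The plan gives no figure to reproduce here. The check is a mapping of the named events onto the stated categories, followed by one illustration of size.

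**Step 1. Map the events.** The inputs are the events in 7.3.2 and 11.1 and the categories in 9.3.

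| Event | Named in | System category in 9.3, by name | Row if non-serious |
|---|---|---|---|
| Infection | 7.3.2, 11.1 | Infectious | Yes |
| Bleeding | 7.3.2, 11.1 | None | No |
| Tissue reaction | 7.3.2 | None | No |
| Rash | 11.1 | None | No |
| Myalgia | 11.1 | None | No |
| Pain | 11.1 | None | No |
| Mild fever | 11.1 | None; infectious if judged a sign of infection | Unclear |

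Of 7 events, 1 fits by name and 7 − 1 = 6 do not. If fever is read as infectious, 5 do not. Fever is not a local event in any case, so the local gap is the other five. Section 11.1 names four of those five (all but tissue reaction), and 7.3.2 names two. Of the three suspension triggers in 7.3.2, 3 − 1 = 2 have no system category. None of the five is a cardiac event, so MACE does not take them in.

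**Step 2. Does the SAE category close the gap?** Only in part. The SAE definition in 10.1 lists outcomes such as life-threatening illness, hospitalization and permanent impairment, and does not refer to grade. Section 7.3.2 acts on grade. The documents therefore allow an event that is Grade 3 and meets no SAE criterion. Such an event suspends enrollment and, if it is bleeding or tissue reaction, has no row in 9.3.

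**Step 3. Bring in 10.1.** There are two readings.
- If 10.1 governs, only serious, research-related events are analyzed. Each then has the SAE row, and the non-serious local event is lost at collection.
- If 6.1.2, 9.3 and Table 4 govern, non-serious related events are evaluated and analyzed, and the local ones are lost at tabulation.

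The event is missing from the report either way, so changing 9.3 alone does not repair it. The exclusion in 10.1 is worded for an enrollment period that the section does not define, which leaves its reach open.

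**Step 4. Size, for illustration.** Take n = 12 (section 5.1.1) and the plan's own Wilson method, with z = 1.96 and z² = 3.84. Assume, purely as an example, that 3 subjects have a non-serious local bleed and nobody has any other related event.
- Existing rows, 0 of 12: the upper limit is z²/(n + z²) = 3.84/15.84 = 0.242, so the interval is 0 to 24.2%.
- A local row, 3 of 12 (p = 0.25): the center is (0.25 + 3.84/24)/(1 + 3.84/12) = 0.410/1.320 = 0.311. The half-width is 1.96 × √(0.25 × 0.75/12 + 3.84/(4 × 144))/1.320 = 0.222. The interval is 8.9% to 53.2%.

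Every table row would show zero events, while the local incidence was 25%.

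**The case against.** The strongest reply has four parts.

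*Some local events are covered.* This stands. Infection at the injection site or stump belongs under the infectious category, and any local event meeting the SAE definition appears under SAE. A reader might infer that local events in general have nowhere to appear. The documents do not support that; the gap is confined to non-serious, non-infectious events.

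*These are not the main risks.* This also stands. Section 11.1 calls the intramuscular injection risks mild and rare and does not rank them as principal. It ties pain, bleeding and infection to the surgical procedure, so some of those events would not be treatment-related and would fall outside the tables anyway. Even so, 7.3.2 treats index-site bleeding and tissue reaction as serious enough to suspend enrollment.

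*Oversight does not run through these tables.* Largely right. A reader might infer that the board would be blind or that the suspension rule would fail. But the rule acts on individual graded events, 6.1.2 puts no category limit on the board's review, and 9.3 says the intervals only assist it. Section 7.1 also has wound infection, debridement and revision recorded separately. Those stump outcomes do not capture injection-site bleeding or tissue reaction, rash, myalgia or harvest-site events. What is damaged is the completeness of the planned summary.

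*This is a small descriptive pilot.* Fair. No decision rule uses the categories and no formal inference is planned, which limits the severity. It does not excuse an incomplete summary of the outcome that the plan puts first.

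Two labels might also be read as errors of substance: MedDRA described as a scale, and MACE listed as a severity. Neither has a shown effect on the analysis.

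**Conclusion.** The gap is real and limited. Treatment-related bleeding, tissue reaction, rash, myalgia and pain that are not serious have no category, listing or interval under 9.3. Two of the three kinds of event that suspend enrollment under 7.3.2 are among them. This follows from a stated rule with fixed categories and not from missing detail.

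The conclusion assumes that the category list is complete as written, that the event is judged treatment-related, and that bleeding is not filed as cardiovascular, which the plan does not say. If bleeding were filed there, the other four would still have no place. How often a Grade 3 local event would meet no SAE criterion cannot be worked out from the documents, so no frequency is claimed; the 3-of-12 example shows only how far the tables could depart from what occurred.

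Section 10.1 is part of the same problem and must be settled together with 9.3. Severity: should-fix.

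**What to change.** In 9.3:
- Add a pre-specified category for local events at the index limb and the marrow harvest site, and a residual category for anything else. Tabulating by MedDRA system organ class would be an acceptable alternative.
- Show CTCAE version 4.0 grade in the tables, so that they can be read against 7.3.2.
- Keep SAE and MACE as flags alongside the categories.
- Apply the planned Wilson intervals to the local category.

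In 10.1: reconcile the limit to serious, research-related events with 9.3, 6.1.2 and Table 4, so that all treatment-related AEs, serious or not, are entered on the case report form and analyzed. Without this the new rows would hold only events already counted as SAEs.

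The cost is wording in two sections, a few more table rows for about 12 subjects, and case report form entry of non-serious related AEs that are already evaluated at Visits 2 to 9. No visits are added.

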## **2.2 Proposed Intended Use Statement**

Human bone marrow preparations induce angiogenesis, decrease muscle fiber apoptosis, and stimulate re-epithelialization of wounds in ischemic hindlimb models in mice. Prior to amputation, bone marrow aspirate will be isolated from patients and concentrated using a BioCue™ device (BMAC), thus presenting a more clinically feasible and potent cell population that may improve tissue perfusion and mitigate ischemic wound complications after amputation.

Concentrated, enriched, autologous, bone marrow aspirate is offered as an option to prevent wound complications after amputation. The BioCue™ device is intended for investigational use only to concentrate BMA by selected investigators familiar with their use and experienced in conducting clinical studies. Human BMAC may only be administered IM to human subjects participating in clinical studies sponsored/approved by Indiana University School of Medicine, and who meet all inclusion criteria and have provided formal written consent.

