**Determine the safety and explore efficacy of BMAC in preventing wound complications in amputations.** In a Phase I trial, BMAC (up to 3 mL) will be injected into the ATM below the point of amputation in the index limb. At the same time BMAC (1 mL) will be injected at up to 25 sites in the proximal leg to promote tissue perfusion before amputation (**Figure 3, Figure 4**). Patients will be scheduled for amputation approximately one week post-injections. Safety will be evaluated by review of treatment related AEs during the 12-month follow-up period. Efficacy will be assessed by rates of wound complications and revision of amputation to historical controls at our institution to assess trends in therapeutic efficacy.

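### Section 9.3 sums adverse-event proportions over two routes of delivery that this single-group, IM-only trial does not have, so the result is not a valid percent incidence

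*Combined protocol and SAP*

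**What the plan says.** The Safety Assessment paragraph of Section 9.3 sets the focus: "Primary attention will focus on the safety of the administration of BMAC as measured by treatment-related AEs". Events are sorted by system ("Three categories of systems are cardiovascular, respiratory, or infectious") and into two severity categories, SAE and MACE. The overlap is declared: "For completeness, instances of AEs may appear in more than one category". Events are listed by frequency within each category. Then, category by category, "the sum and difference between the two routes of delivery of the proportions will be reported as percent incidence".

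The paragraph adds 95% binomial intervals by the Wilson method and p-values for three groups that it does not name. It describes the intervals as a summary and as help for the monitoring board, not as formal inference.

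The rest of the protocol describes a different structure:

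- Section 4.1: "Phase I single center open label trial study that will enroll up to 12 patients".
- Section 2.2: "Human BMAC may only be administered IM to human subjects".
- Section 7.1, after describing the anterior tibialis (ATM) injection: "At the same time BMAC (1 mL) will be injected at up to 25 sites in the proximal leg". Section 3 likewise gives both sets of injections at the same time.

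No section defines a second route or a route-specific group. None says whether the proportions count subjects or events.

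**The concern.** A percent incidence should be the share of treated subjects who had at least one event. Adding two proportions gives that share only when both have the same denominator and no subject appears in both numerators. Nothing in the plan secures this. Since every subject receives both fields, every subject would be in both denominators. A cardiovascular or respiratory event, which falls in two of the three named system categories, cannot be assigned to one field and could be counted under each.

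Treatment-related events are the trial's main safety measure, and the intervals are meant to inform the monitoring board. With at most 12 subjects, a figure of 50% where the share is 25% would change the impression of safety. Section 9.3 also limits the clinical study report to summary analyses, so its readers may be unable to recover the correct share.

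The route difference has the same flaw. If the same subjects are counted under both fields it is zero whatever their number (3/12 − 3/12 = 0). A p-value needs a stated hypothesis about identified groups, and none is given.

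**Working it through.** The plan gives no expected event rate and no safety precision target, so there is no figure to reproduce. The check is direct arithmetic. From the documents come N = 12 (Section 4.1), both injection fields in every subject (Sections 3 and 7.1), and the 95% Wilson interval (Section 9.3). Event counts and the sizes of any separate groups are not given, so those below are assumptions for illustration.

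**Correct quantity.** Share = subjects with at least one event ÷ 12. The Wilson interval is [p + z²/2n ± z√(p(1−p)/n + z²/4n²)] ÷ (1 + z²/n). For 3/12 with z = 1.96:

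- centre term: 0.25 + 0.1601 = 0.4101
- half-width term: 1.96 × √(0.015625 + 0.006669) = 0.2927
- divisor: 1.3201
- interval: 8.9% to 53.2%

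**Reading A: the routes are the two injection fields, same 12 subjects.** Let *a* and *b* be the subjects counted under each field and *c* those counted under both.

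- Planned sum = (a + b)/12
- Share affected = (a + b − c)/12
- Ratio = (a + b)/(a + b − c). This is 1 when c = 0 and 2 when a = b = c.

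| a, b, c | Sum | Share | Ratio |
|---|---|---|---|
| 3, 3, 0 | 50% | 50% | 1.0 |
| 3, 2, 1 | 41.7% | 33.3% | 1.25 |
| 3, 3, 3 | 50% | 25% | 2.0 |
| 7, 7, 7 | 116.7% | 58.3% | 2.0 |

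The last sum is 14/12. It is not a proportion, and no binomial interval applies to it.

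**Reading B: the routes are two separate groups.** With equal sizes n, x₁/n + x₂/n = 2 × (x₁ + x₂)/2n, which is always exactly twice the pooled incidence. For example, 1/6 + 2/6 = 50% against 3/12 = 25%. With unequal sizes the ratio varies:

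- 3/8 + 0/4 = 37.5% against 25% (ratio 1.5)
- 0/8 + 3/4 = 75% against 25% (ratio 3)
- 0/11 + 1/1 = 100% against 1/12 = 8.3% (ratio 12)

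The documents describe no such groups.

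**Category overlap.** Suppose 3 subjects each have one infectious SAE. The infectious line reads 3/12 and the SAE line reads 3/12, and each is correct. Because the sum is formed within a category, overlap adds nothing to it. Only a total across categories (6/12 against 3/12) would double-count, and none is planned.

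**Subjects or events.** If events were the numerator, 3 subjects with 2 events each would read 6/12 = 50% (Wilson 25.4% to 74.6%) instead of 3/12 = 25% (8.9% to 53.2%). The plan does not say which is meant. The binomial interval is valid only for the subject count.

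**The case against.** The best defence is that the sum is loose wording for the two routes pooled. That would also explain the three groups as route one, route two and both together. But the text speaks of a sum of proportions, and even the pooled reading needs two route groups, which the design lacks. Alternatively, the three groups could be the three system categories. Those are overlapping classes of event, not groups of subjects, and p-values for them would still lack a stated hypothesis.

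A second defence is that little depends on the figure. Much of this stands. The sum is added to listings by category, and the intervals are declared descriptive. The stopping and suspension rules in Section 7.3.2 are triggered by individual graded events, not by a percentage. With 12 subjects, a board that sees event-level data can recover the correct count. Section 9.3 says that earlier trials reported no adverse events with BMAC, and Section 10.1 restricts what is collected and analysed to serious, research-related events. Counts may therefore be low, and 7 of 12 subjects is a remote case. If there are no events, the sum and the share are both zero.

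Three stronger readings are tempting, and the documents do not support them:

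- *That listing an event in several categories inflates the figure.* The overlap is openly stated and leaves each category's figure unchanged.
- *That the reported percentage is certain to be inflated, or always doubled.* If different subjects are counted under the two fields, the sum equals the share affected. Exact doubling holds for equal separate groups or for complete overlap between fields.
- *That event counts are the planned numerator, or that the sum is the trial's headline safety result.* The plan leaves the numerator unspecified and names no single safety figure.

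**Conclusion.** Wrong as written. Section 9.3 gives a rule for the percent incidence that matches nothing in the design and cannot be relied on to yield an incidence. The sum, the difference and the p-values all depend on routes or groups that do not exist; possible inflation follows from that.

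Its size depends on a reading the plan does not settle. Over two injection fields in the same subjects it is 1 to 2 times the share affected. For equal separate groups it is exactly 2, and for unequal groups it can be lower or higher. A value above 100% is possible in either case. The event counts behind these figures are assumed, while the single group, single route and shared subjects come from the documents.

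This should be corrected before the safety tables are produced. Its consequence is limited to how safety is described and read; no formal inference and no stopping decision depends on it.

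**What to change.** In the Safety Assessment paragraph of Section 9.3:

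1. Delete the route sum, the route difference and the p-values for the three groups. Removing the sum alone would leave a comparison between routes that do not exist.
2. For each category, and in one overall line, report the number and percent of all injected subjects with at least one treatment-related adverse event. Count each subject once per line and attach a Wilson 95% interval. For example, 3 of 12 reads 25.0% (8.9% to 53.2%) and 1 of 12 reads 8.3% (1.5% to 35.4%).
3. State that the categories overlap and must not be added together.
4. List event instances separately, without intervals.

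The cost is a wording change and one extra table line, with no new data. The only loss is a comparison by delivery route, which this design cannot support.
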